4.1 OVERVIEW OF STUDY DESIGN/INTERVENTION

4.2 Design

Patients with progressive castrate resistant metastatic prostate cancer are eligible to register for this study, providing all other eligibility criteria are met. Patients can be co-registered to therapeutic clinical trials, but may not receive any therapeutic treatments associated with those trials within 4 weeks prior to our imaging study.

We have based our selection of a 10 mg starting dose on the lack of cross reactivity of the STEAP1 antigen in normal human tissues and work with other antibodies reported in the literature. Cross-reactivity of MSTP2109A antibody with normal and binding affinity was similar between cynomolgus monkey and human, the cynomolgus monkey serves as a pharmacologically relevant model to predict human pharmacokinetics. DSTP3086A demonstrated pharmacokinetic linearity in cynomolgus monkey over the tested dose range of 0.3-5.0 mg/kg. Therefore it is expected that there will be no antibody sink to

rapidly clear the antibody injected. An amount of 10 mg is expected to be adequate for tumor imaging. The rationale for 10 mg is based on the fact that this is an amount that has been used successfully with other antibodies that have minimal or minor cross reactivity with normal tissues *in vivo* (Divgi, Pandit-Taskar et al. 2007; Carrasquillo, Pandit-Taskar et al. 2011). Nonetheless, since no pharmacokinetic or imaging studies have been performed with ^{89}Zr -DFO-MSTP2109A, initial studies must determine an acceptable mass for imaging. In order to streamline antibody mass selection, initial Cohort 1A patients (up to 6 in cohort) will receive 10 mg of ^{89}Zr -DFO-MSTP2109A and will undergo pharmacokinetics and serial imaging. Decision of whether to study a second cohort, Cohort 1B, at a higher dose (20 mg) will be based predominantly on the basis of whether adequate tumor targeting is observed (tumor detection in >75% of STEAP1 positive patients). As secondary measure we will evaluate for unexpected normal organ accumulation, based on PET imaging and evidence of rapid plasma clearance based on pharmacokinetic parameters and tumor targeting. If adequate tumor targeting is achieved we will use the starting dose of 10 mg in patients enrolled in Cohort 2. The absence of antigen sink may be confirmed if pharmacokinetics show Vd of less than 3 times plasma volume, T1/2 is greater than 50 h and if visually there is no binding to normal tissues above that expected from blood pool. If there is suggestion of antigen sink, and inadequate tumor targeting, we will evaluate an additional 6 patients who will receive total dose of 20 mg (Cohort 1B). The patients in Cohort 1B also will undergo pharmacokinetics, imaging and whole body measurements as outlined for the 10 mg cohort in section 9.0. Once the milligram dose to be administered is selected, a second group of patients (Cohort 2) consisting of up to 15 patients will be enrolled, that will have only 1 whole-body scan, at a time point to be determined based on the results of Cohort 1A or 1B patients.

Because ^{89}Zr -DFO-MSTP2109A has not been evaluated in patients, toxicity assessment will be performed using Common Terminology Criteria for Adverse Events (CTCAE) v4.

4.3 Intervention

The intervention is the administration of a single dose of the ^{89}Zr -DFO-MSTP2109A tracer for imaging purposes. In Cohort 1A or 1B, after administration of the experimental tracer, the patient will undergo up to four PET scans during the 7 days post injection, whole body probe measurements and pharmacokinetics. In Cohort 2, patients will undergo injection of ^{89}Zr -DFO-MSTP2109A, and they will undergo one PET scan from top of skull to mid thigh (this may be adjusted based on known extent of disease) and no pharmacokinetics will be performed. The primary population will be those who are planning to enroll in the therapeutic trial using DSTP3086S (11-016), although for Cohort 1A, 1B and potentially Cohort 2 patients that meet the inclusion criteria may be enrolled even if not considered for DSTP3086S therapy. No clinical management decisions will be made based on ^{89}Zr -DFO- MSTP2109A imaging. Patients may not be re-imaged on this trial.

5.0 THERAPEUTIC/DIAGNOSTIC AGENTS

MSTP2109A is a humanized antibody that targets STEAP1 that will be labeled with ^{89}Zr . We will use ^{89}Zr , a positron-emitting radionuclide, labeled to MSTP2109A via DFO. This protocol will explore the feasibility of ^{89}Zr -DFO-MSTP2109A PET imaging; the tracer's pharmacokinetic (PK) and biodistribution properties; its ability to detect disease relative to standard imaging modalities.

Drug Accountability

MEMORIAL SLOAN-KETTERING CANCER CENTER IRB PROTOCOL

IRB#:12-178 A(3)

The investigator is obliged to keep sufficient documentation of the delivery and use of the investigational product. The documentation will include administration date/ time, calibration date/time, quantity, patient code, lot number and date of destruction. The investigator should maintain records that document adequately that the patients were provided the dose specified in the protocol and reconcile the medication received for the study. The label of each vial will contain the patient code and lot number, patient and radiopharmaceutical information will be entered in the radiopharmacy drug accountability forms. The investigator may assign some or all of the investigator's duties for drug accountability to an appropriate individual such as pharmacist or nuclear medicine technician who is under the supervision of the investigator.

⁸⁹Zr-DFO-MSTP2109A

Radiolabeling of ⁸⁹Zr-DFO-MSTP2109A: The **DFO-MSTP2109A** will be labeled in accordance with the MSKCC investigator sponsored IND. The study will be performed under an FDA approved IND for ⁸⁹Zr-DFO-MSTP2109A, no studies will be performed until the IND is approved. The final product will contain up to 5 mCi and will have been brought up to desired total antibody quantity (e.g. 10 or 20 mg) of DFO-MSTP2109A by adding cold carrier dfo-MSTP2109A as outlined in the design section. The product will have met the release criteria specified in the IND. Immunoreactivity and sterility assays will be performed post release.

The investigational product label will include the patient name, MRN and the calibration date and time. The investigational product is to be used within 8 hours of manufacturing.

Package Labeling and Formulation

Each vial will contain the following information on the label: ⁸⁹Zr-DFO-MSTP2109A

1 vial (10 mL) contains: up to 5 mCi / ~10 ML

Calibration date: <insert time>(EST)_on <insert date>_

Must use within 8 hours of manufacturing!

Excipients: Human serum albumin; sodium phosphate

Lot : <insert lot number>

Patient Name: <insert patient code>

Clinical study MSKCC IRB #:<insert IRB#>

PI: <insert PI name >

Caution: New Drug Limited to Investigational Use by Qualified Investigator Only
STORE AT 2°C-8°C IN A REFRIGERATOR or up to 4h at room temperature.

DO NOT USE IF CLOUDY OR CONTAINS PARTICULATE MATTER

Manufactured by: Radiochemistry Core MSKCC

Images will be corrected for attenuation and scatter and adjusted for system sensitivity and providing parametric images in terms of standardized uptake values (SUV) (= μ Ci found/gm tissue / (μ Ci injected/gm body mass)).

6.1 CRITERIA FOR SUBJECT ELIGIBILITY

6.2 Subject Inclusion Criteria

To be included in this study, patients should be eligible for enrollment into protocol 11-016 (therapy with the DSTP3086S ADC) or meet all of the following criteria:

- Patients meeting the criteria for enrollment on research protocol 11-016 to receive

MEMORIAL SLOAN-KETTERING CANCER CENTER IRB PROTOCOL

IRB#:12-178 A(3)

DSTP3086S ADC (therapeutic ADC based on MSTP2109A) will be the preferred patients for this study. Patients that are to receive DSTP3086S will not be injected with DSTP2086S until imaging with ⁸⁹Zr-DFO-MSTP2109A is finished, approximately 1 week.

- Adult male >21years of age
- Visible lesions by either CT, bone scan or MRI consistent with metastatic disease
 - Metastatic progressive disease
 - Imaging modalities:
Bone scan: new osseous lesion and/or
MRI or CT: An increase in measurable soft tissue disease or the appearance of new sites of disease.

Or

PSA Changes	Minimum No. of determinations	Interval	Percentage increase over range of values
Androgen independent	3	\geq 1Week	25%
	2	\geq 2Week	

- Patients with histologically confirmed prostate cancer at MSKCC
- STEAP1 antigen positive tissue known from prior IHC testing or if STEAP1 status is not known archival sample will be sent to Genentech for IHC. Samples need to be positive, when feasible metastatic lesions will be tested preferentially rather than the primary.
- Performance status of 60 or higher (Karnofsky scale) (Appendix A)
- Ability to understand and willingness to sign a written informed consent document
- PSA levels to be taken within 2 weeks of antibody administration.

6.3 Subject Exclusion Criteria

Patients meeting any of the following exclusion criteria will not be eligible for study entry:

- Previous anaphylactic reaction to human, humanized or chimeric antibody
- Hematologic
 - Platelets <75K/mcL
 - ANC <1.0 K/mcL
- Hepatic laboratory values
 - Bilirubin >1.5 x ULN (institutional upper limits of normal)
 - AST/ALT >2.5 x ULN
- Renal laboratory values
 - eGFR < 30mL/min/1.73m²
- Patients with history of hypersensitivity reaction to any component of ⁸⁹Zr-DFO-MSTP2109A, including DFO.

7.0 RECRUITMENT PLAN

Recruitment Plan (with Limited Waiver of Authorization)

A member of the 11-016 clinical trial or the patient's treatment team at MSKCC will identify potential study participants. Men of all races and ethnic groups will be considered for study participation. Candidates must conform to all inclusion and exclusion criteria to be accepted into the study.

If the investigator is a member of the treatment team, s/he will screen their patients' medical records for suitable research study participants and discuss the study and their potential for enrolling in the research study. Potential subjects contacted by their treating physician will be referred to the investigator/ research staff of the study.

The principal investigator may also screen the medical records of patients with whom they do not have a treatment relationship for the limited purpose of identifying patients who would be eligible to enroll in the study and to record appropriate contact information in order to approach these patients regarding the possibility of enrolling in the study.

During the initial conversation between the investigator/ research staff and the patient, the patient may be asked to provide certain health information that is necessary to the recruitment and enrollment process. The investigator/ research staff may also review portions of their medical records at MSKCC in order to further assess eligibility. They will use the information provided by the patient and/or medical record to confirm that the patient is eligible and to contact the patient regarding study enrollment. If the patient turns out to be ineligible for the research study, the research staff will destroy all information collected on the patient during the initial conversation and medical records review, except for any information that must be maintained for screening log purposes.

In most cases, the initial contact with the prospective subject will be conducted by either the treatment team, investigator or the research staff working in consultation with the treatment team. The recruitment process outlined presents no more than minimal risk to the privacy of the patients who are screened and minimal protected health information (PHI) will be maintained as part of a screening log. For these reasons, we seek a (partial) limited waiver of authorization for the purposes of (1) reviewing medical records to identify potential research subjects and obtain information relevant to the enrollment process; (2) conversing with patients regarding possible enrollment; (3) handling of PHI contained within those records and provided by the potential subjects; and (4) maintaining information in a screening log of patients approached (if applicable).

Estimated breakdown of target population

% Native American/Alaskan	0%
% Asian/Pacific Islander	1%
% Black Non Hispanic	3%
% Hispanic	1%
% White Non-Hispanic	94%
% Other	1%

8.1 PRETREATMENT EVALUATION

- History and physical examination
- Laboratory studies (within 2 weeks before study entry):
 - Complete blood count
 - PSA

MEMORIAL SLOAN-KETTERING CANCER CENTER IRB PROTOCOL

IRB#:12-178 A(3)

- Serum BUN, creatinine, AST, ALT, total bilirubin, alkaline phosphatase, and albumin
- eGFR assessment
- Standard clinically indicated imaging studies (within 4 weeks before study entry or up to 2 weeks after entry, provided the patient has not received treatment). No intervening new therapy is allowed between conventional imaging studies and the ⁸⁹Zr-DFO-MSTP2109A
 - Bone scintigraphy
 - CT of chest, abdomen, and pelvis with contrast, unless contraindicated on clinical grounds (allergy or renal insufficiency). MRI is acceptable if CT is clinically contraindicated
 - Modified MRI of the pelvis, if clinically indicated
- If STEAP1 status is not known from prior testing patient archival tissue will be sent to Genentech to determine presence of STEAP1 antigen..

9.1 TREATMENT/INTERVENTION PLAN

9.2 Pharmacokinetics

Patients are not required to fast before ⁸⁹Zr-DFO-MSTP2109A injection or imaging.

Catheter insertion and Pharmacokinetics

If feasible, 2 intravenous catheters (Hep-Lock) will be placed by staff in the Nuclear Medicine department for radiopharmaceutical administration and blood sampling, or alternatively a central line may be used for injection or sampling. The intravenous catheter will be removed at the conclusion of the imaging session. If two lines are not feasible, one line will be used for both injection and PK sampling with intervening 10 cc saline flush and change of catheter hub. Patients in Cohort 2 (no pharmacokinetics, will not require a second catheter).

⁸⁹Zr-DFO-MSTP2109A: To determine clearance and for metabolite analysis of the drug, Cohort 1A and 1B patients (up to 6 patients per cohort) receiving ⁸⁹Zr-DFO-MSTP2109A will have serial blood samples drawn. Blood samples will be obtained in green top tube:

- Just prior to injection of ⁸⁹Zr-DFO-MSTP2109A (baseline)
- Approximately 5 ± 2, 15 ± 5, 30 ± 9, 60 ± 19, and 120 to 240 minutes after injection of the tracer.
- One sample at the time of each subsequent day of imaging (24 ± 8h, ~48-96h and ~120-168h post injection).

These data are used to determine the time-activity curves for plasma (% injected dose/liter). Blood is centrifuged, and the plasma pipetted and counted. Samples may be tested for breakdown products by TCA or HPLC. Blood will also be aliquoted for sampling, if in the first 3 patients no binding is observed to blood elements only plasma sampling will be counted in subsequent patients.

For each blood sample, 4-6 mL of blood will be drawn in green top tubes.

Patients in Cohort 2 will undergo injection and 1 imaging session, but no pharmacokinetics will be performed.

9.3 Imaging

^{89}Zr -DFO-MSTP2109A

Radiolabeling of ^{89}Zr -DFO-MSTP2109A: The **DFO-MSTP2109A** will be labeled in accordance with the MSKCC investigator sponsored IND. The study will be performed under an FDA approved IND for ^{89}Zr -DFO-MSTP2109A, no studies will be performed until the IND is approved. The final product will contain up to 5 mCi and will have been brought up to desired total antibody quantity (e.g. 10 or 20 mg) of DFO-MSTP2109A by adding cold carrier dfo-MSTP2109A as outlined in the design section. The product will have met the release criteria specified in the IND. Immunoreactivity and sterility assays will be performed post release.

The investigational product label will include the patient name, MRN and the calibration date and time. The investigational product is to be used within 8 hours of manufacturing.

PET scanning: In order to provide reproducible clinical data, we will acquire all ^{89}Zr -DFO-MSTP2109A PET scans on the GE PET-CT scanner DSTE at MSKCC or the same or a newer generation scanner. Once a study is begun in one scanner, it will be continued on the same scanner unless malfunction/emergency issues prevent this. Intravenous injection of ^{89}Zr -DFO-MSTP2109A (maximum of 5 mCi \pm 10%) will be given over 5-15 minutes. Initially we will start with \sim 5 mCi of ^{89}Zr -DFO-MSTP2109A; the activity may be adjusted downward based on visual review of image quality. A PET-CT scan extending from top of skull to mid thighs will be performed to determine the biodistribution. The low dose CT portion of the ^{89}Zr -DFO-MSTP2109A on the first day will utilize 80 mA (low mA) and on subsequent days, we will use 10 mA in order to minimize radiation exposure. In order to minimize imaging time, lower limbs will be included only for patients with known lesions in lower limbs on previous imaging and if at least 5 other lesions are not identified in the torso.

Active lesions will be identified (Nuclear Medicine investigator and MM) based on conventional images and those thought to represent active disease based on review of the patients conventional images and treatment history (ie external radiation) will be considered as lesions for determination of antibody localization. A lesion will be considered present if there is greater localization than that expected based on blood pool distribution of the tracer. Given that at present we do not know the heterogeneity of the antigen between lesions or between primary and metastatic disease a patient will be considered positive if any of the active lesions are identified with the ^{89}Zr -DFO-MSTP2109A. We will, nonetheless tabulate the number of lesions and their status based on ^{89}Zr -DFO-MSTP2109A. When pathologic material that has been evaluated for the presence of STEAP1 is available for any specific lesion, we will correlate the presence of STEAP1 with imaging results.

Patients in Cohort 1A (and if performed Cohort 1B) will also have imaging at 4 time points post-injection to allow for selection of optimal imaging time and dosimetry determination. For these patients, top of skull to mid thigh scans will be acquired:

- Within one to four hours following injection of tracer on Day 1
- \sim 24 \pm 8 hours post-injection (Day 2)
- \sim 48–96 hours post-injection (once during Days 3–5)
- \sim 120–168 hours post injection (once during Days 6–8)

MEMORIAL SLOAN-KETTERING CANCER CENTER IRB PROTOCOL

IRB#:12-178 A(3)

Images will be analyzed with ROI and SUVmean and max measurements will be obtained. The serial quantitative data obtained over the various organs of interest (heart, liver, spleen, kidney, lung and any other organ that exhibits uptake will be collected. These data can then be utilized to determine organ time activity curves and the dosimetry can be calculated. Uptake and clearance values will be summarized using descriptive statistics (mean, median standard deviation. Once the biodistribution and pharmacokinetics have been characterized, subsequent patients will not require serial imaging and pharmacokinetics, but rather will have a single scan at an optimal time point determined based on the patients in cohort 1A and or cohort 1B. We will determine the time at which the greatest number of lesions are seen. This is likely to be between 3-8 days, but choice will be based on the first Cohort 1 patients' data, using the most frequent day at which the most lesions are seen and/or at times at which best contrast is observed determined visually. Thus, for the remainder of the patients in Cohort 2, PET scan will be performed once. The timing of this scan will be determined based on findings from Cohort 1A and/or 1B, as described above.

Infusion reactions with MSTP2109A intact IgG have not been evaluated. Infusion reaction to the ADC DSTP3086S antibody drug conjugate in 18 patient treated thus far have been minor and not clinically significant (i.e. none or Gr1). In the event of fever, rigors, shortness of breath, or other evidence of infusion reaction, patients may receive diphenhydramine 25-50 mg IV and Tylenol 650 mg PO as felt to be clinically appropriate by the treating physician. The emission data are typically acquired for 3–10 minutes per bed position depending upon the time post-injection and visual quality of the images. Index lesions will be identified based on the patient's conventional diagnostic imaging.

Images will be stored as Digital Imaging and Communications in Medicine (DICOM) on the PACS and HERMES. Images to be sent out to Genentech will be burned on a CD or equivalent by patient. All images will be anonymized according to institutional policy with the patients code used as identifiers.

No decision on the patients' health care management will be made on the basis of Imaging with ⁸⁹Zr-DFO-MSTP2109A.

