2.2 Secondary Objectives

- To determine the better/"adequate" ⁸⁹Zr-DFO-MSTP2109A mass amount for tumor imaging (10 or 20 mg) .
- To determine optimal time relative to ⁸⁹Zr-DFO-MSTP2109A administration for tumor imaging.
- To use quantitative biodistribution data of ⁸⁹Zr-DFO-MSTP2109A uptake to perform dosimetry estimates.
- To correlate ⁸⁹Zr-DFO-MSTP2109A uptake in tumors with STEAP1 antigen expression by IHC
- To explore whether ⁸⁹Zr-DFO-MSTP2109A PET imaging results are related to patient outcome in patients being treated with DSTP3086S.

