12.0 CRITERIA FOR THERAPEUTIC RESPONSE/OUTCOME ASSESSMENT

Positive lesions on ⁸⁹Zr-DFO-MSTP2109A will be defined visually as a focus of accumulation of radioactivity that is deemed to not be physiologic and is higher than adjacent or contralateral background. Antibody scan will be read blinded from clinical history and conventional imaging modalities. Two different experienced, blinded readers will visually analyze the ⁸⁹Zr-DFO-MSTP2109A scans, and SUVmax/mean will be determined in lesions identified and in normal organs and blood pool. To study the accumulation and biodistribution of ⁸⁹Zr-DFO-MSTP2109A in patients with progressive prostate cancer, the accumulation of ⁸⁹Zr-DFO-MSTP2109A will be assessed for each site and compared with the baseline radionuclide bone scan, FDG PET/CT, CT, and/or MRI imaging. The definition of a positive lesion will be a lesion identified by an experienced reader on conventional imaging CT/MRI, bone scan, and/or FDG scan consistent with metastatic disease, as is currently done clinically. Lesions on ⁸⁹Zr-DFO-MSTP2109A or conventional imaging will be read in a scale of 1 to 5, 1= negative, 2 = probably negative, 3= not sure, 4= probably positive and 5= definitively positive. Once this is done, a consensus master list of lesions will be created that compares all imaging conventional imaging modalities(CT/MRI, FDG PET, bone scan), only those lesions that are conspicuously positive (i.e., "4 or 5") by imaging will be considered as a positive site of disease. Discrepant findings between findings on conventional imaging and ⁸⁹Zr-DFO-MSTP2109A modalities will be considered false positive or false negative. Although it would be ideal to biopsy any site that is considered abnormal this is not logistically feasible or ethically acceptable. Successful imaging will be considered a sensitivity of detection of $\geq 75\%$ of patients that are STEAP1 positive. One or 2 non-blinded readers (access to clinical, laboratory and imaging data) will identify "positive lesions".

As a first level, we will compare site by site. Since the individual modalities are based on different mechanisms of uptake, they may not have exact correspondence in space, since bone scan is a 2D modality and looks at bone reaction and ⁸⁹Zr looks at tumor antigen expression and is a 3D modality.

For this purpose, we have made a list of standardized anatomic sites, to make sure that a positive

MEMORIAL SLOAN-KETTERING CANCER CENTER IRB PROTOCOL

IRB#:12-178 A(3)

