14.1 BIOSTATISTICS

14.2 Primary Objective

The primary objective of this protocol is to determine the feasibility, safety and tolerability of single dose administration of ^{89}Zr -DFO-MSTP2109A antibody.

A patient with STEAP1 positive tumor will be considered antibody-imaging-positive if 20% or more of the active lesions are detectable (STEAP1 positivity is an eligibility criterion for protocol 11-016 which forms the basis of eligibility for this protocol; see section 6 for details). Active lesion means any lesion that was identified by conventional imaging methods and clinical data at baseline. We have selected a low threshold of 20% for this first imaging study for 3 reasons: 1) we do not know what the heterogeneity of antigen expression is within a number of lesions in the same patient; 2) we will consider positive any lesion based on conventional clinical imaging criteria, in which case some lesions considered positive may be false positive and more importantly 3) our main emphasis is to evaluate whether patients whose tumor images are positive with ^{89}Zr -DFO-MSTP2109A are more likely to have a response to the antibody based drug conjugate used under

MEMORIAL SLOAN-KETTERING CANCER CENTER IRB PROTOCOL

IRB#:12-178 A(3)

protocol 11-016. Thus, we do not want to discard this agent if we can use it as a **theranostic** (defined as an agent that is integrated into the drug development process so as to guide patient selection and drug development) for the development of the antibody base drug conjugate being used under protocol 11-016. Nonethe less, we intend to evaluate treatment response of all available lesions in this way we will maximize our ability to determine the relationship between uptake of antibody and response.

If, for any patient, there is evidence of an “antigen sink” based on rapid clearance < 50 h or $Vd > 3$ times plasma volume, we will consider a patient antibody-imaging-positive if 20% or more of the active lesions are visualized. The presence of an “antigen sink” may bind a significant amount of antibody and make less available for binding to tumor.

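### The planned IHC comparison uses STEAP1 presence, which does not vary in the qualifying samples, so it does not relate uptake to expression as objective 2.2 intends

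*Combined protocol and SAP*

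**What the plan says.** All references are to the combined protocol and SAP.

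- **Objective.** Section 2.2 lists, as a secondary objective, correlating "uptake in tumors with STEAP1 antigen expression by IHC".
- **Analysis.** Section 9.3 gives the only analysis text. It applies "When pathologic material that has been evaluated for the presence of STEAP1 is available for any specific lesion", and then "we will correlate the presence of STEAP1 with imaging results". It names no statistic, IHC score or uptake measure for this comparison.
- **Eligibility.** Section 6.2 gives two routes in. The listed criteria state: "Samples need to be positive, when feasible metastatic lesions will be tested preferentially rather than the primary". For the other route, section 14.2 states that "STEAP1 positivity is an eligibility criterion for protocol 11-016 which forms the basis of eligibility for this protocol".
- **IHC request.** Section 8.1 says that, where status is unknown, "archival tissue will be sent to Genentech to determine presence of STEAP1 antigen". No intensity score, H-score or positivity cut-off is given.
- **Other tissue.** Section 9.3 concedes that "at present we do not know the heterogeneity of the antigen between lesions or between primary and metastatic disease". Section 12.0 adds: "Although it would be ideal to biopsy any site that is considered abnormal this is not logistically feasible or ethically acceptable". Section 17.1 mentions optional biopsies once, in a sentence on costs, with no procedure or number.
- **Secondary analyses.** Section 14.3 covers uptake summaries adjusted for clustering and the relation of imaging to response under 11-016. It does not mention the IHC objective.

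**The concern.** The objective concerns two quantities that can differ between STEAP1-positive tumours: how much tracer a lesion takes up and how strongly it expresses the antigen. The analysis replaces expression with presence and uptake with an unspecified imaging result. Patients are then selected on presence, so the explanatory variable is fixed in the tissue that every patient is sure to have.

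What is at stake is the trial's own rationale. Sections 1.0 and 3.2.2 want the tracer because it may show both whether the target is there and how intensely. Intensity is the part that can still vary after selection on positivity, and it is the part that the planned comparison leaves out.

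**Working it through.** **The plan's own figure.** There is none to reproduce. The documents give no sample size, alpha, power or precision for the IHC objective, and no number of lesion-matched samples.

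**Inputs.** Section 4.2 allows up to 6 patients in Cohort 1A, 6 more in Cohort 1B if it opens, and up to 15 in Cohort 2. The maximum is 6 + 15 = 21 without Cohort 1B and 6 + 6 + 15 = 27 with it. Table 2 also runs to a 27th patient.

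**Step 1: qualifying samples only.** Code presence as x = 1 for a positive sample and x = 0 for a negative one. By either entry route x = 1 for every patient, so Var(x) = 0. The coefficient r = Cov(x, y) / (SD(x) SD(y)) is then 0/0, undefined at any n. A 2 × 2 table of presence by imaging has an empty row, and its Fisher p is 1.0 whatever the scans show.

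**Step 2: suppose some other lesions test negative.** The documents plan no test, so this only illustrates how much information there would be. Assume that n lesions are evaluated, one per patient. Assume also that k are IHC-negative and none of these is seen on PET, and that about 75% of the positives are seen. With u positives unseen, the two-sided Fisher p here equals C(u + k, k) / C(n, k).

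| k negative | n = 21 | n = 27 |
|---|---|---|
| 1 | 6/21 = 0.29 | 7/27 = 0.26 |
| 2 | 21/210 = 0.10 | 28/351 = 0.08 |
| 3 | 35/1330 = 0.03 | 84/2925 = 0.03 |
| 4 | 70/5985 = 0.01 | 210/17550 = 0.01 |

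On these assumptions, about three incidental negatives would be needed before the comparison said much. The plan has no mechanism to produce them.

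**Step 3: what a graded measure could deliver.** Assume one independent sample per patient and two-sided alpha 0.05. By the Fisher z approximation, the correlation detectable with 80% power is tanh((1.96 + 0.84) / √(n − 3)).

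- n = 27: tanh(2.80 / 4.90) = 0.52
- n = 21: tanh(2.80 / 4.24) = 0.58
- n = 15: tanh(2.80 / 3.46) = 0.67
- n = 6: tanh(2.80 / 1.73) = 0.92

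If the observed r were 0.5, the 95% interval tanh(atanh 0.5 ± 1.96 / √(n − 3)) would be 0.09 to 0.77 at n = 21 and 0.15 to 0.74 at n = 27. The smaller n values matter because the number of lesions with matched tissue is unknown. The formula is for an ordinary correlation and is only a guide for a rank correlation.

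**The case against.** The strongest reply is that the requirement for positivity governs the sample that qualifies the patient, whereas the analysis in 9.3 is by lesion. A patient who qualifies on one positive block, possibly from the primary, may have a metastasis that tests negative. The protocol says heterogeneity is unknown, and optional biopsies are mentioned. This stands. A reader might infer that every evaluated sample must be positive and that the objective therefore cannot be answered; the documents do not support that. Presence is fixed in the qualifying samples, not in all tissue. The objective itself speaks of uptake and expression, both of which can vary among positive tumours. What does not stand is reliance on incidental negatives, since nothing in the plan sets out to collect them.

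A second reply is that the protocol uses *correlate* loosely. Section 14.3 applies it to Kaplan-Meier estimates, for example. On that reading, an all-positive set still gives the proportion of IHC-positive lesions seen on PET. That is fair, and it is a usable descriptive result. It measures detection, though, and does not relate uptake to expression.

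A reader might also infer that a single negative sample could never give a significant result, even with perfect separation. That is true for an assumed n of 15 (1/15 = 0.067), but the documents state no such n. At 21 or 27 the minimum is 1/21 = 0.048 or 1/27 = 0.037. With no alpha or test planned, nothing here depends on that threshold.

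**Conclusion.** The concern holds as a mismatch between objective and analysis. In the qualifying samples the stated variable has zero variance. Elsewhere the comparison depends on tissue that is available by chance and tests negative. The planned analysis can therefore report at most a detection proportion among IHC-positive lesions.

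This conclusion rests on the eligibility text applying to all enrolled patients and on there being no IHC scoring plan beyond what the documents show. The figures in steps 2 and 3 of the check rest on the assumptions stated there. The objective is secondary, and no cohort decision or primary conclusion changes. This is an inexpensive improvement, not a flaw that threatens the trial.

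**What to change.** In 9.3, with a matching paragraph in 14.3:

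1. Replace presence with the graded IHC result (intensity or H-score), and name the score.
2. Relate it to SUVmax of the same lesion by rank correlation, with an interval that allows for clustering by patient. Report it as a descriptive estimate, without a significance claim.
3. Measure SUVmax at every lesion with evaluated tissue, whether or not PET shows it. Section 12.0 collects SUV in lesions identified, which could be read as leaving out the unseen ones.
4. Show lesion-matched tissue separately from primary or unmatched archival tissue, since 6.2 permits either.
5. Keep the proportion of IHC-positive lesions seen on PET as a separate, labelled summary.
6. State that selection on positivity restricts the range and that the results do not extend to STEAP1-negative disease.

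The cost is a short text change plus obtaining and recording a grade. No new tissue is needed, but the change assumes that the laboratory's reading provides a grade, which the documents do not confirm. If it does not, the plan should say that only the detection proportion will be reported and that the relation of uptake to expression will not be assessed. The remaining downside is low precision, as the check shows.
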